6.3. Secondary Efficacy Endpoints and Analyses

The secondary efficacy endpoints are listed in Section 1.2. Analyses will be based on the FAS and PP analysis set.

As exploratory analyses, endpoints analyzed using an ANCOVA method will be also analyzed using MMRM method in a manner analogous to the analysis as described in Section 6.2.3.2.

6.3.1. Proportion of Patients with a $\geq 50\%$ Reduction from Baseline in the Monthly Average Number of CH Attacks During the 12-Week Period After the First Dose of the IMP

This secondary efficacy endpoint will be analyzed using Cochran-Mantel-Haenszel (CMH) test stratified by baseline preventive medication use (yes or no). Descriptive statistics (count and percent) and p-value for Row Mean Scores difference will be presented.

The 12-week period is the period from administration of the first dose of the IMP to the EOT/early withdrawal visit. CH attacks within the 12-week period will be derived from the e-diary data as described in Section 6.1.1 and prorated to 28. Missing data handling methods are provided in Section 6.1.4.2.

The proportion of reduction for a patient will be calculated using formula [2]. Responders will be those with $\geq 50\%$ reduction.

Example SAS code for CMH:

```
PROC FREQ DATA=<name>;
    TABLES BPMU*TRTP*AVALC / CMH;
    OUTPUT OUT=<name> CMH;
RUN;
```

Where TRTP denotes the planned treatment group; BPMU denotes the baseline preventive medication use (yes or no); and AVALC denotes the responses with yes for responders (with $\geq 50\%$ CH attacks reduction) and no for non-responders (with $< 50\%$ CH attacks reduction).

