#### **9.5.4.3. Secondary and Exploratory Efficacy Analysis**

The continuous endpoints will be analyzed using an ANCOVA or a mixed model for repeated measures. For the proportion of responders, defined as 50% or more reduction from baseline in the monthly average number of CH attacks, data will be analyzed using a Cochran-Mantel-Haenszel test stratified by baseline preventive medication use (yes/no).

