2.2. Randomization and Blinding

Patients will be randomly assigned with stratification based on gender, country, and baseline concomitant preventive medication use (yes or no) in a 1:1:1 ratio to 1 of 3 treatment groups.

- **fremanezumab 900-mg intravenous (iv) loading dose group:** fremanezumab at 900 mg administered via an approximately 1-hour iv infusion and 3 placebo subcutaneous (sc) injections at visit 2 (week 0) followed by fremanezumab at 225 mg administered as single sc injections (225 mg/1.5 mL) at visits 3 and 4 (weeks 4 and 8, respectively)
- **fremanezumab 675-mg sc loading dose group:** placebo administered via an approximately 1-hour iv infusion and fremanezumab at 675 mg administered as 3 sc injections (225 mg/1.5 mL) at visit 2 (week 0) followed by fremanezumab at 225 mg administered as single sc injections (225 mg/1.5 mL) at visits 3 and 4 (weeks 4 and 8, respectively)
- **placebo group:** placebo administered via an approximately 1-hour iv infusion and 3 placebo sc injections at visit 2 (week 0) followed by placebo administered as single sc injections at visits 3 and 4 (weeks 4 and 8, respectively)

The sponsor, investigators, study staff (except for staff involved in bioanalytical analyses and interim analyses [by a third-party, unblinded statistician]), and patients will be blinded to treatment assignment throughout the study.

Randomization will be performed using electronic interactive response technology (IRT), a third-party vendor. The randomization code will be generated by IRT following specifications from the Biostatistics Department. A Teva statistician will be responsible for reviewing the dummy randomization codes, and the final randomization code will be maintained by the third-party vendor in a secure location.

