4.3. Region of Pooled Countries

The study is planned to be conducted in approximately 12 countries. The countries will be pooled to 2 regions (US/Canada and other).

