6.2.2. Primary Efficacy Analysis

The hypothesis testing for the primary analysis is:

$$H_o : \delta_1 = \delta_2 \quad \text{vs} \quad H_a : \delta_1 \neq \delta_2$$

where δ_1 and δ_2 are the estimates of mean change from baseline in the monthly average number of CH attacks for the fremanezumab treatment group and the placebo group, respectively. To control overall type I error rate, the comparison of each active treatment group (fremanezumab 900-mg iv loading dose group and fremanezumab 675-mg sc loading dose group) versus the placebo will be tested using Hochberg's step-up method as described in Section 7.

The primary endpoint will be analyzed using an ANCOVA method. The model will include baseline preventive medication use (yes or no), gender, region (US/Canada or other), and treatment as fixed effects; the baseline number of CH attacks as a covariate. The least square (LS) mean and SE for each treatment group, LS means and corresponding 95% confidence intervals for the treatment differences (fremanezumab - placebo), and associated p-values will be presented.

The analysis will be performed on the FAS and PP analysis sets.

Example SAS code for ANCOVA

```
PROC MIXED DATA=<name>;
  CLASS TRTP SEX REGION BPMU;
  MODEL CHG= BASE BPMU SEX REGION TRTP /S ;
  LSMEANS TRTP /DIFF=CONTROL(("Placebo")) CL ALPHA=0.05;
  ODS OUTPUT LSMEANS= <name> DIFFS= < name> ;
RUN;
```

Where TRTP denotes the planned treatment group; BPMU denotes the baseline preventive medication use (yes or no); CHG denotes the change from baseline; and BASE denotes the baseline number of CH attacks. In bold are the SAS key words.

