Use of oxygen will be recorded in the e-diary. The 12-week period is the period from administration of the first dose of the IMP to the EOT/early withdrawal visit. The weekly average number of days using oxygen for a patient during the 12-week period will be calculated and prorated to 7 days using formula [1B]. Missing data handling method is provided in Section 6.1.4.2.

Data will be analyzed using an ANCOVA method in a manner analogous to the primary endpoint as described in Section 6.2.2.

6.3.5. Patient-Perceived Satisfactory Improvement at 1, 4, 8, and 12 Weeks After Administration of the First Dose of the IMP Relative to Baseline

The PPSI scale will be completed in the e-diary at home at week 1(day 7) and in the investigational site tablet at the visits 2, 3, 4, and 5. Patients will mark the level of CH-associated pain and indicate the level of pain using the following scale compared with 4 weeks ago:

- 1 = Much worse
- 2 = Moderately worse
- 3 = Slightly worse
- 4 = Unchanged
- 5 = Slightly improved
- 6 = Moderately improved

- 7 = Much improved

PPSI will be defined as change in pain that corresponds with a minimal rating of “slightly improved” (Protocol Section 6.7). For analysis purpose, a dichotomous scale of “Responder” (scales 5 to 7) or “Non-responder” (scales 1 to 4) will be derived.

The percentage of patients in dichotomous scale of “Responder” or “Non-responder” at week 1, visit 3, 4, and 5 will be analyzed using a CMH method in a manner analogous to the first secondary endpoint as described in Section 6.3.1.

Modification to SAS code in Section 6.3.1: adding a ‘by’ statement for visit.

Raw scales will be summarized using descriptive statistics. A missing category will be presented if applicable.

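### The CMH tests for the ≥50% responder endpoint and PPSI leave out gender and geography; if either predicts response, the tests are valid but somewhat conservative and give up a few points of power

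*SAP*

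**What the plan says.** **Randomisation (SAP 2.2).** "Patients will be randomly assigned with stratification based on gender, country, and baseline concomitant preventive medication use (yes or no) in a 1:1:1 ratio". SAP 4.3 adds: "The study is planned to be conducted in approximately 12 countries", pooled for analysis into US/Canada and other.

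**Primary model (SAP 6.2.2).** The ANCOVA has "baseline preventive medication use (yes or no), gender, region (US/Canada or other), and treatment as fixed effects", with the baseline attack count as covariate. The MMRM (SAP 6.2.3.2) and the triptan/ergot and oxygen endpoints (SAP 6.3.3 and 6.3.4) carry the same factors.

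**Responder endpoint.** SAP 6.3.1 says that this endpoint "will be analyzed using Cochran-Mantel-Haenszel (CMH) test stratified by baseline preventive medication use (yes or no"), with no other factor, and its example code reads BPMU\*TRTP\*AVALC. Protocol 9.5.4.3 agrees: "data will be analyzed using a Cochran-Mantel-Haenszel test stratified by baseline preventive medication use (yes/no").

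**Tests that inherit the method.** For PPSI, SAP 6.3.5 says that the responder percentages "will be analyzed using a CMH method in a manner analogous to the first secondary endpoint as described in Section 6.3.1". The exploratory 75% and 100% responder endpoints (SAP 6.4.1) and PGIC (SAP 6.4.9.6) do the same.

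**Testing order (SAP 7).** Secondaries follow the order of SAP 1.2, and testing continues only while both active arms reach p ≤ 0.05. The ≥50% responder endpoint comes first after the primary. PPSI is last, at week 12 only.

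**The concern.** Stratified randomisation makes the arms alike in gender and country mix. If those factors predict response, the true variance of the treatment comparison is smaller than it would be under simple randomisation. A test that ignores the factors still uses the larger variance. It then rejects less often than its nominal 5% under the null and less often than it could under the alternative.

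The plan accounts for gender and region in every model for a continuous endpoint and drops both in the tests for binary endpoints. What is at stake is the chance of passing the first secondary endpoint, and with it access to all later ones.

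**Working it through.** **1. The plan's own figure.** The only stated power is for the primary endpoint (SAP 2.4): difference 4, SD 8, two-sided 0.05, 90% power.

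n per arm = 2(1.960 + 1.282)² × 8² / 4² = 84.06, so 85, against 86 stated. Power at 86 = Φ(4 / (8√(2/86)) − 1.960) = Φ(1.319) = 90.6%. Allowing for dropout, 258 / 0.86 = 300. The figure reproduces and this point does not affect it. Neither document gives a power, or a current response rate, for the responder or PPSI tests.

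**2. The test.** For one active arm against placebo, in stratum s with n₁ active, n₀ placebo, n in total and m responders, of whom a are on active:

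E = n₁m/n; V = n₁n₀m(n − m) / (n²(n − 1)); χ² = (Σ(a − E))² / ΣV, compared with 3.84.

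**3. Size of the conservatism.** With arms balanced in every randomisation cell, the true null variance is proportional to the average of p(1 − p) over cells. The planned test uses the average of p̄(1 − p̄) over the two medication strata. Hence type I error ≈ 2(1 − Φ(1.96 √(planned/true))).

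Assumptions, none from the documents: 12 countries of unequal size, 68% in one gender category, 60% on preventives, 30% reference response, medication odds ratio (OR) 1.5.

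- Moderate (gender OR 2, country logit SD 0.5): planned 0.2252, true 0.2095; 1.96 × √(0.2252/0.2095) = 2.03; type I error about 0.042.
- Strong (gender OR 3, country logit SD 1.0): planned 0.2345, true 0.1859; 1.96 × √(0.2345/0.1859) = 2.20; type I error about 0.028.

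Balance is not perfect in practice, so the true loss should be slightly smaller.

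**4. Simulation on the same assumptions.** 300 randomised, permuted blocks of 3 within country × gender × medication, 10,000 trials per row, treatment OR 2.25. Columns: planned 2 strata / 8 strata (medication × gender × two regions) / 48 cells (all countries).

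| Gender and country effect | Type I error | Pairwise power |
|---|---|---|
| None | 0.051 / 0.051 / 0.052 | 79.6 / 79.5 / 77.5% |
| Moderate | 0.044 / 0.046 / 0.050 | 74.7 / 75.4 / 75.5% |
| Strong | 0.031 / 0.035 / 0.052 | 61.6 / 64.2 / 68.9% |

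With 258 randomised (4,000 trials per row), the 8-strata test changes power by −0.35, +1.5 and +2.75 points and the 48-cell test by −2.9, +0.4 and +7.3.

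**5. Other assumption sets.** Here the geographic effect lies wholly between the two regions, with gender and region each at the OR shown. Entries are 2 strata / 8 strata.

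| Set | OR | Type I error | Pairwise power |
|---|---|---|---|
| A: treatment OR 2.33, 6,000 trials | 1 | 4.8 / 4.8% | 83.3 / 83.1% |
| A | 2 | 4.5 / 4.9% | 79.8 / 81.3% |
| A | 3 | 3.8 / 4.8% | 75.6 / 79.3% |
| B: marginal rates held at 30% v 50%, 10,000 trials | 1 | not reported | 82.7 / 82.5% |
| B | 2 | not reported | 84.5 / 85.4% |
| B | 3 | 3.8% (planned) | 86.6 / 88.9% |

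In set A, power for both arms together, which is what SAP 7 requires before moving on, was 73.6 / 73.4%, 68.3 / 70.4% and 62.6 / 67.4%.

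**6. Large effects.** Under the superseded assumption of 30% v 60% (treatment OR 3.5; used only as an illustration), the assumptions of step 4 give 99.1 / 99.2%, 98.3 / 98.3% and 95.1 / 95.7% for 2 and 8 strata. The gain is below one point throughout.

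**7. Stratum sizes.** A pairwise comparison has about 200 patients. Eight strata average 200/8 = 25. With an assumed 30% women and 35% US/Canada, women in US/Canada number 200 × 0.30 × 0.35 = 21, or about 10 per medication stratum. The full cross-classification has 12 × 2 × 2 = 48 cells, or 200/48 ≈ 4 patients each. In the simulations 2.7 to 4% of patients fell in cells with only one arm.

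**The case against.** The planned test is prespecified, stated consistently in the protocol and SAP, and valid. The effect is conditional on prognostic strengths that the documents never give, and every rate and odds ratio above is assumed. At moderate strength the gain is only about 0.7 to 1.5 points with 300 randomised. The responder endpoint is tested only after both primary comparisons succeed, PPSI comes last, and SAP 6.4.1 and 6.4.9.6 lie outside the testing sequence. All of this stands, and it limits the point to efficiency.

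It can also be said that the remedy does not use the factor left out, since randomisation is by country and not by region. That stands too. Where country effects were strong and spread across countries, eight strata moved type I error only from 0.031 to 0.035. The primary ANCOVA has the same limitation, so it would be wrong to infer that it carries all three randomisation factors in full.

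What the objection does not supply is a reason for the binary endpoints to ignore factors that the plan adjusts for elsewhere. Nor does it show a material cost of including them.

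**Conclusion.** The point holds as a modest, conditional loss of efficiency. If gender or region predicts response, the planned CMH has type I error of about 3 to 4.5% and gives up roughly 1 to 4 points of pairwise power. In the set where it was examined, the loss was about 2 to 5 points for passing the responder gate in both arms. If neither factor is prognostic, eight strata gain nothing and cost about 0.2 points with 300 randomised (0.35 in the smaller run at 258). The ranges rest on assumed response rates, gender and region mix, block size and prognostic strengths.

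A reader might infer that dropping stratification factors inflates the false-positive rate, or that the tests are bound to be underpowered. Neither is supported. No simulation showed inflation of the planned test beyond noise, and the documents do not say whether gender or country is prognostic.

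**What to change.** In SAP 6.3.1 and 6.3.5, stratify the CMH by preventive use, gender and region (TABLES BPMU\*SEX\*REGION\*TRTP\*AVALC / CMH), applied to each active arm against placebo. For consistency, do the same in the exploratory SAP 6.4.1 and 6.4.9.6. Protocol 9.5.4.3 and the synopsis name a single stratification factor, so SAP 17, which now lists no changes, should record the departure before unblinding.

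Do not stratify by individual country. The roughly 48 sparse cells lost 2 to 3 points of power when the factors were not prognostic, although they recovered more when country effects were strong. Region is the practical compromise and recovers only part of any country effect.

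The cost is a line of text and code in each section, an entry in SAP 17, and some strata nearer 10 patients than 25. Small strata carry little weight in a CMH test. If the single factor is kept, the SAP should say why.

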7. MULTIPLE COMPARISONS AND MULTIPLICITY

Hochberg's step-up method will be implemented to test primary and secondary endpoints while controlling the overall type 1 error rate at 0.05.

The treatment comparisons will be for the fremanezumab 900-mg iv loading dose group versus placebo [H_{01}] and the fremanezumab 675-mg sc loading dose group versus placebo [H_{02}]. According to Hochberg step-up method, the rules of multiple comparisons for 2 null hypotheses for the primary endpoint are as follows:

1. If the resulting 2-sided p-values from both comparisons are ≤ 0.05 (reject both null hypotheses), then the next comparison of interest will be interpreted inferentially at the alpha level of 0.05 and statistical significance will be claimed for both active dose groups. Testing of secondary efficacy measures will be continued.
2. If the resulting 2-sided p-value from 1 of comparisons is > 0.05 (fail to reject the null hypothesis) and other resulting 2-sided p-value is ≤ 0.025 ($\frac{\alpha}{2} = 0.025$; reject the null hypothesis), then the result from the comparison with p-value ≤ 0.025 will be interpreted inferentially at the alpha level of 0.05, and statistical significance will be claimed for this active dose group. No further comparisons will be interpreted inferentially.
3. If the resulting 2-sided p-value from both comparisons are > 0.05 (fail to reject both null hypotheses), then no statistical significant will be claimed and no comparisons will be interpreted inferentially.

If the resulting 2-sided p-values from both comparisons for the primary endpoint are ≤ 0.05 (reject both hypotheses; case 1 as described above), testing of secondary efficacy measures will proceed at an error rate of 0.05 in the sequential manner as specified in Section 1.2. The same testing rules as described above will be followed. This process will continue either until all comparisons of interest for secondary endpoints are interpreted inferentially or until the point at which the resulting 2-sided p-value for a comparison of interest is > 0.05 . At the point where a 2-sided p-value > 0.05 , the testing process stops. No further comparisons will be interpreted inferentially.

For the last secondary endpoint (PPSI assessments), only the assessment at week 12 will be included in the multiple comparisons.

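### Does the CMH specification for the responder and PPSI endpoints leave the Section 7 testing rules without the two p-values they need?

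*SAP*

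**What the plan says.** SAP 6.3.1 analyses the proportion of patients with at least a 50% reduction by a Cochran-Mantel-Haenszel test stratified by baseline preventive medication use (yes or no). On output it asks for counts and percentages, and adds that a "p-value for Row Mean Scores difference will be presented". The example SAS code contains "TABLES BPMU*TRTP*AVALC / CMH", where TRTP is the planned treatment group. It has no WHERE or BY statement on treatment, and the input dataset is a placeholder name.

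SAP 6.3.5 has the dichotomised PPSI "analyzed using a CMH method in a manner analogous to the first secondary endpoint as described in Section 6.3.1". The only code change it lists is a BY statement for visit.

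SAP Section 7 sets out what is tested. It opens "The treatment comparisons will be for the fremanezumab 900-mg iv loading dose group" against placebo (H01) and adds the 675-mg sc group against placebo (H02). Its rules are written for a pair of p-values: both at or below 0.05, or one above 0.05 and the other at or below 0.025. For the secondaries, taken in the order of SAP 1.2, it says "The same testing rules as described above will be followed". For PPSI, "only the assessment at week 12 will be included in the multiple comparisons". Protocol 9.6 has the same two hypotheses and rules.

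For the primary ANCOVA, SAP 6.2.2 is explicit about the pairs: "LS means and corresponding 95% confidence intervals for the treatment differences (fremanezumab - placebo), and associated p-values will be presented".

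**The concern.** Read alone, 6.3.1 appears to specify the wrong test for a confirmatory endpoint. With three treatment rows and a yes/no response, Row Mean Scores has 2 degrees of freedom and asks whether the arms differ in any way. It does not say which regimen differs from placebo, or in which direction. The ANCOVA and MMRM sections both ask for fremanezumab-minus-placebo differences with p-values. The CMH sections do not, and protocol 9.5.4.3 names only the stratified test.

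The responder endpoint is the first step after the primary, so its result decides whether the other secondaries are tested at all. PPSI at week 12 is the last step. If the overall p-value were used at these steps, the sequence could continue when one regimen had not beaten placebo, or stop when both had.

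**Working it through.** **The plan's own figure.** SAP 2.4 gives 86 evaluable per arm for at least 90% power at a difference of 4 and SD 8, two-sided 0.05. The noncentral t gives power 0.903 at 86 per arm (0.8999 at 85), and 258/(1 − 0.14) = 300. This reproduces. It concerns the primary endpoint; the current plan states no power or responder rates for the CMH endpoints.

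**Can the overall and pairwise tests disagree?** Assume 100 per arm in two identical strata, so n = 50 per arm per stratum. With N patients and m responders in a stratum, and x responders in an arm, the stratum contributes

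(N − 1)/N × Σ(x − nm/N)² / [n(m/N)(1 − m/N)],

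and two identical strata double it.

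*Observed rates 42/42/28% (iv/sc/placebo), i.e. 21, 21, 14 per stratum.*
- Three arms: N = 150, m = 56, expected 18.67 each. Sum of squares 32.67, divided by 50 × 0.3733 × 0.6267 = 11.70, gives 2.793. Then × 149/150 × 2 gives Q = 5.55 on 2 df, p = 0.062.
- Each pair: N = 100, m = 35, deviations ±3.5. 24.5/11.375 = 2.154; × 99/100 × 2 gives Q = 4.26 on 1 df, p = 0.039.

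*Observed rates 18/38/28%, i.e. 9, 19, 14 per stratum.*
- Three arms: m = 42, deviations −5, 5, 0. 50/10.08 = 4.960; × 149/150 × 2 gives Q = 9.85, p = 0.007.
- Pairs: Q = 2.80, p = 0.095 (iv) and Q = 2.24, p = 0.135 (sc).

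So the tests can disagree in either direction.

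**How often, if the overall test were substituted?** Trials were simulated with 86 per arm and both regimens at the design effect on the primary. Responder status was correlated 0 to 0.8 with attack change. Both primary p-values are at or below 0.05 in about 84% of trials. Among those, the overall test is significant while at least one pairwise test is not in:

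| Assumed true rates, % (two regimens / placebo) | Share of trials |
|---|---|
| 45/45/30 | 19–20% |
| 50/50/30 | 14–17% |
| 50/40/30 | 42–43% |
| 60/60/30 | 1–2% |

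The reverse (both pairs significant, overall not) occurs in at most 1.3%.

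**Does the plan lead to that substitution?** Set the sections side by side.
- Section 7 needs a p-value for H01 and one for H02 at every step. An overall p-value is neither, and rules comparing two p-values with 0.05 and 0.025 cannot be run on one number.
- Section 7 is the only place that says how confirmatory claims are made, and it extends its rules to the secondaries expressly. Section 6.3.1 says what is presented; it does not say that the overall test replaces the two comparisons.
- If the placeholder dataset holds one regimen plus placebo, the same TABLES statement gives a 1-df Row Mean Scores test for that pair. With two arms and a binary response, the three CMH statistics SAS prints (correlation, row mean scores, general association) coincide, so no choice among them remains.
- The SAP's example code needs the surrounding text elsewhere too. The MMRM example in 6.2.3.2 requests all pairwise differences, and the prose narrows them to fremanezumab minus placebo. Reading the CMH code with Section 7 is the same step.

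**The case for a change.** The strongest reply is that Section 7 shows two p-values are needed but not how they are obtained. The prose of 6.3.1, as well as the code, describes a single p-value. The SAP does spell out code changes elsewhere (BY statements for subgroups and visits, revised LSMEANS lines), yet gives none here. A model-based contrast, or a pairwise contrast using the three-arm variance, might also be chosen, and a confirmatory step should not leave that open.

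The textual part stands: no section says in so many words that the CMH test is run by pair. The part about competing methods is weaker. The protocol and SAP both name the CMH test, so a regression contrast would depart from the plan. A three-arm-variance contrast is not what the named procedure prints. It also differs little in the borderline example. For 42 versus 28, the difference summed over strata is 14 and its variance is 2 × 56 × 94 × 100/(150 × 149) = 47.1. So 14²/47.1 = 4.16, p = 0.041, against 0.039 from the two-arm test.

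The 18/38/28 example shows that the tests differ mathematically, but it is remote where it would matter. It puts one regimen 10 points below placebo on responders after both regimens have already won on attack counts from the same diary. In a gated simulation at the design effect, a regimen at least that far below placebo occurred in 0 to 0.4% of trials.

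**Conclusion.** The concern does not call for a change. SAP 6.3.1 and 6.3.5 omit a detail: that the stratified CMH test is run once for each regimen against placebo. Section 7 and protocol 9.6 supply it by naming the two hypotheses and carrying the two-p-value rules through the secondaries. An analyst following the whole plan arrives at two 1-df CMH tests for the responder endpoint and two for PPSI at week 12. A three-arm p-value, if tabulated as well, has no role in the confirmatory sequence.

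The disagreement rates of 1 to 43% are therefore hypothetical. They require the analyst to set Section 7 aside, and they depend on responder rates that the current plan does not state. The conclusion rests on reading the code as the example it is labelled to be and on Section 7 governing the confirmatory claims. The stratification, the Hochberg rules and the sample size are unaffected.
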